#### 6.4 Pharmacokinetics

No pharmacokinetic data will be collected in this study.

## 6.5 Safety

Safety analyses will be conducted on treated subjects by as-treated treatment group (i.e., the actual treatment received) and All BHV-3500.

Safety measures will include: AEs, laboratory tests, vital signs, physical measurements, electrocardiograms (ECGs), S-STS, and nasal inspection.

Analysis periods are pre-treatment and on-treatment (see Section 7.4).

Values and changes from baseline in safety findings (e.g., laboratory tests, vital signs and physical measurements, ECGs) and S-STS endpoints will be summarized as continuous variables descriptively at baseline and the end of treatment visit. These analyses will be based on observed data without imputation and regardless of rescue medication use. For the change from baseline, subjects must have non-missing paired measurements at baseline and end of treatment visit to be evaluable. If a subject has multiple values in the end of treatment analysis window (see Section 7.5), then the last non-missing value in the analysis period will be used; in the case of a tie, the value collected from the central laboratory, if applicable, will be used.

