¹ Screening Phase will be 3 - 28 days. Subject should be entered in the IWRS once they sign the informed consent form to obtain their study subject identification code.

²The **Baseline**/ **Randomization Visit** may only occur *after* all screening procedures are completed and the subject meets all inclusion/exclusion criteria. If the subject does not meet all eligibility requirements, the subject should be screen failed in the IWRS.

³ Subjects will use their assigned eCOA handheld device to answer questions about their migraine symptoms upon experiencing a moderate or severe migraine headache. The subject will administer study drug or matching placebo if the following criteria are met: 1) the headache remains moderate or severe; 2) the subject has completed all required migraine assessment questions in the handheld, including their current most bothersome migraine symptom, and 3) the subject has not already taken prohibited medications (see protocol section 5.4).

⁴ Subjects should keep track of their concomitant and rescue medications on the appropriate study paper diary provided throughout the study. These diaries should be returned to the investigational site for review and electronic data capture (EDC) entry.

⁵ The randomization visit is considered day 1 out of the 45 days subjects have to treat and report a migraine in their handheld device. Subjects will be randomized in the IWRS and will be stratified by answering "yes" or "no" to prophylactic migraine medication use in the IWRS.

⁶Nasal inspection – The nasal passages and turbinates will be visually inspected with a nasal speculum or otoscope at the screening, baseline and end of treatment visits to detect evidence of nasal inflammation or edema.

⁷ Height will only be captured at the Screening Visit. Weight, body temperature, respiratory rate, blood pressure and heart rate will be collected at all time points where indicated. Sitting arterial systolic and diastolic blood pressure and pulse rate will be measured.

- ⁸ SAEs are reported from the time of signed informed consent and non-serious AEs are reported from baseline. All ongoing non-serious AEs and SAEs will be followed to resolution or until the Investigator deems there will be no further status change. SAEs that occur during the treatment period should be reported to site in real time. Non-serious AEs that occur during the treatment period should be reported to the site at the EOT.

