4.3.4 End of Treatment Visit

Subjects will return to the site for their End of Treatment Visit (after assessments in the handheld are completed) within 7 (+2) days after dosing with study medication. The "+2" day window is included for scheduling purposes only.

At the End of Treatment Visit, medication compliance, monitoring of tolerability and safety assessments (including vital signs, laboratory tests, nasal inspection and electrocardiography) will be performed. Refer to Table 1 for a full list of assessments completed at the EOT.

If a subject has NOT experienced a migraine headache of moderate or severe intensity within 45 days after randomization, they are still required to complete all EOT visit procedures. All subjects must return used and unused study medication and their handheld device to the investigational site.

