8.1.5 Potential Drug Induced Liver Injury (DILI)

Wherever possible, timely confirmation of the initial liver-related laboratory abnormalities should occur prior to the reporting of a potential DILI event. All occurrences of potential DILIs, meeting the defined criteria, must be reported as SAEs as per Section 8.1.2.

Potential drug induced liver injury is defined as:

1. Aminotransferases (AT) (ALT or AST) elevation > 3 times the upper limit of normal (ULN)

AND

2. Total bilirubin (TBL) > 2 times ULN, without initial findings of cholestasis (elevated serum alkaline phosphatase)

AND

3. No other immediately apparent possible causes of AT elevation and hyperbilirubinemia, including but not limited to, viral hepatitis, pre-existing chronic or acute liver disease, or the administration of other drug(s) known to be hepatotoxic.

If any potential DILI is identified and meets the criteria above, the Biohaven Medical Monitor (or designee) should immediately be contacted for further instruction on dosing adjustments and whether the subject must discontinue from the trial and appropriate follow up requirements.

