# 6.5.5 Sheehan-Suicidality Tracking Scale (S-STS)

The S-STS is a prospective, self-reported rating scale that contains 16 questions to track both treatment-emergent suicidal ideation and behaviors. In the event the subject is unavailable, the S-STS clinician-administered rating scale will be completed that contains 6 yes/no questions.

Self-reported S-STS scores are calculated as follows:

- Ideation subscale score: Sum of scores (0-4) for Questions 2-11
- Behavior subscale score: Sum of scores (0-4) for Questions 1a, (highest of 12 or any row of 16), (highest of 14 or any row of 15), 17, and 20
- Total score: Sum of the ideation and behavior subscale scores.

Values and changes from baseline in the self-reported S-STS ideation subscale, behavior subscale, and total score will be summarized as continuous variables at baseline and the end of treatment visit. The number and percentage of subjects in each change from baseline category (i.e., < -1, -1, no change, 1, > 1) will also be presented for the ideation subscale, behavior subscale, and total score.

The by-subject S-STS listing will include study visit and assessment date. If the total score > 0, then responses to all questions will be presented; otherwise, only the ideation subscale, behavioral subscale, and total scores will be presented.

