## 7.4 Analysis Periods

Analysis periods are defined as follows:

- Pre-treatment: measurement date/time at or before the study drug start date/time. This period is used to derive baseline values and to assess pre-treatment endpoints.
- On-treatment: measurement date/time after the study drug start date/time. Note that AEs with imputed start date equal to the study drug start date are part of this period.
- On-study: measurement date/time after the randomization date/time.

See Section 7.3 for derived dates for determining analysis periods.

If measurement time is missing or not collected for a parameter, then the measurement date will be compared to the derived date.

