# 7.5 Analysis Visit Windows

Study days are calculated from the IWRS randomization date as follows:

- Measurement date randomization date + 1, if measurement date ≥ randomization date
- Measurement date randomization date, if measurement date < randomization date.

Treatment days are calculated from the study drug start date as follows:

- Measurement date study drug start date +1, if measurement date  $\geq$  study drug start date
- Measurement date study drug start date, if measurement date < study drug start date.

Analysis windows for safety and outcomes research parameters are presented in Table 4.

For longitudinal analyses of safety and outcomes research parameters, the end of treatment analysis visit window is defined as measurement date/time > study drug start date/time.

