# Table 4: Analysis Windows for Safety and Outcomes Research Parameters

Evaluation	Analysis-Specified Interval
Screening	≤ Study Day -1
Randomization	Study Day 1
Post-Randomization	≥ Study Day 2

See Section 7.6.3.2 for efficacy analysis windows.

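### The end-of-treatment safety value is the latest one in a post-dose window with no upper limit, so a follow-up repeat can displace the scheduled visit's result in the value and change-from-baseline summaries

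*SAP*

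**What the plan says.** The protocol has one safety visit after the single dose. Section 4.3.4 places it "within 7 (+2) days after dosing with study medication".

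SAP 6.5 summarises values and changes from baseline as continuous variables at baseline and at that visit, for laboratory tests, vital signs and physical measurements, ECG and S-STS. Where a subject has more than one value in the EOT window, "then the last non-missing value in the analysis period will be used". The preference for the central laboratory only breaks ties.

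The window is set in SAP 7.5: "the end of treatment analysis visit window is defined as measurement date/time > study drug start date/time". SAP 7.4 is equally open: "On-treatment: measurement date/time after the study drug start date/time". SAP Table 4 has no EOT row, and its last row, "Post-Randomization ≥ Study Day 2", also has no end.

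The protocol gives reasons for measurements after the EOT visit. Table 1, footnote 8: "All ongoing non-serious AEs and SAEs will be followed to resolution or until the Investigator deems there will be no further status change". Section 8.1.5 expects that, wherever possible, "timely confirmation of the initial liver-related laboratory abnormalities should occur prior to the reporting of a potential DILI event". SAP 6.5.2 analyses local as well as central laboratory results.

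**The concern.** The tables are labelled as EOT-visit results, but the rule does not tie them to that visit. A subject whose EOT result is normal has little reason to be tested again and keeps the EOT value. A subject whose result is abnormal may well be retested, and the retest then stands in for the visit. Which subjects have their value replaced thus depends on the result itself.

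What is at stake is whether the mean value and mean change at EOT describe the subjects about a week after dosing, or a mixture of that time and later follow-up. If one arm had more abnormal results, and so more repeats, the descriptive comparison between arms would be affected too.

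**Working it through.** The documents give no figure to reproduce, so the check sets the rule against the visit schedule and then against each safety output.

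**1. Does a later repeat fall in the window?** SAP 7.5 counts treatment days as measurement date minus study drug start date, plus 1. An EOT visit 7 days after dosing is treatment day 8; with the 2-day allowance, the latest is day 9 + 1 = 10. Suppose ALT is 5 x ULN on day 8 and 0.8 x ULN on day 30. Both are after dosing, so both are in the EOT window. The day-30 value is the later one and enters the EOT mean and the change from baseline. Nothing in SAP 6.5, 7.4, 7.5 or Table 4 limits the window to day 10, excludes unscheduled tests or prefers the scheduled visit.

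**2. Which outputs use the selected value?**
- Affected: values and changes for laboratory tests (6.5.2.3), vital signs and physical measurements (6.5.3.1) and ECG (6.5.4.1), and the S-STS values, changes and change categories (6.5.5).
- Not affected: laboratory grades and shifts (6.5.2.1), liver-test elevations, ALT/AST shifts and the eDISH plot (6.5.2.2), vital-sign and weight abnormalities (6.5.3.2), ECG shift and QTc categories (6.5.4.2 and 6.5.4.3), nasal inspection (6.5.6), AE tables and the by-subject listings. These use the worst or any on-treatment value, or show the results. The 5 x ULN value above still counts in them.

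**3. How large could the effect be?** Let f be the fraction of an arm whose EOT value is replaced, a the EOT value, r the repeat and b the baseline, with all other subjects unchanged.
- Mean change with the scheduled value: f x (a - b)
- Mean change with the latest value: f x (r - b)
- Difference: f x (a - r)

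Arm size from SAP 5: 0.95 x 400 = 380. Every other input is an assumption: b = 0.5 x ULN and r = 0.8 x ULN.

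| f | subjects (f x 380) | a (x ULN) | scheduled value | latest value | difference (x ULN) |
|---|---|---|---|---|---|
| 0.5% | 1.9 | 3 | 0.0125 | 0.0015 | 0.011 |
| 1% | 3.8 | 5 | 0.045 | 0.003 | 0.042 |
| 2% | 7.6 | 10 | 0.190 | 0.006 | 0.184 |

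The first and last rows are the ends of the range for f from 0.5% to 2% and a from 3 to 10 x ULN. In absolute units, a resolved excess of 100 U/L (also assumed) in 1% of an arm gives 0.01 x 100 = 1 U/L, and in 3% gives 0.03 x 100 = 3 U/L.

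**4. Is the direction fixed?** No. The difference is positive when r < a and negative when r > a. With f = 1%, a = 3 and r = 5 it is 0.01 x (3 - 5) = -0.02 x ULN, so the rule would then move the mean away from baseline. For the comparison between arms, what matters is how f x (a - r) differs between them. If it is equal, the difference between arms does not change.

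**5. S-STS.** Protocol Table 1 schedules the scale at screening, baseline and EOT only. For a score above 0, Protocol 6.2.5 calls for evaluation by the investigator, not for a repeat rating. If a repeat were nevertheless recorded, it would replace the EOT score in the SAP 6.5.5 output for "The number and percentage of subjects in each change from baseline category". Its recall period under Protocol 6.2.5 would start at the EOT visit, so it would not cover the time from dosing to that visit.

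**The case against.** The strongest reply is that little depends on these tables. The laboratory part of the safety objective concerns the frequency of clinically relevant abnormalities. SAP 6.5.2 identifies clinically significant ones as grade 3 to 4, and 6.5.2.1 tabulates them from the worst on-treatment value. Mean changes are descriptive and untested. The follow-up provisions concern AEs and potential liver injury; they set no schedule of repeat laboratory tests, vital signs or ECGs after EOT, and a confirmatory liver test may still be elevated. An unscheduled test before the EOT visit is correctly superseded by the visit. All of this stands and keeps the point minor. It does not answer why a day-30 value should be reported as the EOT visit.

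A reader might infer three stronger things that the documents do not support:
- **That abnormal results disappear from the safety report.** They stay in every output listed as unaffected in the working.
- **That the rule always pulls towards no drug effect.** It takes the latest value whichever way that value has moved. The lean comes from who is likely to be retested, and the number of retests is not known.
- **That positive suicidality scores will be tabulated as no change.** That needs a repeat score, which no section schedules or asks for. The S-STS listing in SAP 6.5.5 gives all responses when the total is above 0, suicidality AEs have their own table (6.5.1.3), and the narratives listing (6.5.7) flags them.

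**Conclusion.** The point holds at minor severity. As written, SAP 6.5 and 7.5 let any later repeat in the database stand as the EOT-visit value in the continuous value and change summaries for laboratory tests, vital signs and physical measurements, and ECG. The same would apply to S-STS if a score were repeated.

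The expected lean towards baseline rests on one assumption: that repeats follow abnormal results more often than normal ones, and that those results tend to resolve. Its size cannot be derived from the documents. The illustrative range of 0.011 to 0.184 x ULN in an arm's mean ALT change rests on assumed inputs. No test or stated decision rule depends on these summaries.

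**What to change.** In SAP 6.5 and 7.5, use the result from the scheduled EOT visit for the EOT value and change summaries. If it is missing, use the non-missing post-dose value nearest to that visit. Keep the central-laboratory rule for ties. Keep later unscheduled repeats for the listings and worst-value tables, which need no change. Optionally, add the worst post-dose S-STS score (ideation, behavior and total) to SAP 6.5.5, so that this scale has a worst-value summary as the laboratory and ECG data do.

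The cost is a few lines of SAP text and a small programming change, plus one short output if the S-STS option is taken. No new data and no protocol amendment are needed. Making the change before unblinding avoids a later choice about which value counts as EOT.

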#### 6.5.1 Adverse E vents

AEs will be displayed in tables and listings by SOC and PT, unless specified otherwise. AEs by SOC and PT will be displayed in descending order of overall frequency within SOC and PT.

See Section 7.6.1 for AE start date imputation, AE counting rules in frequency tables, treatment-emergent adverse events (TEAEs), and AEs of special interest.

The following by-subject listings of all AEs will be provided for enrolled subjects: AEs; deaths; SAEs; and AEs leading to study drug discontinuation. TEAEs will be flagged.

#### 6.5.1.1 AE Overview

An AE overview without SOC and PT will present the number and percentage of subjects with any of the following AEs: any AE; mild AE; moderate AE; severe AE; AE related to study drug; SAE; SAE related to study drug; AE leading to study drug discontinuation; and AE leading to death.

An AE overview will be produced for each analysis period (pre-treatment, on-treatment) for treated subjects.

An AE will be considered related to study drug if the relationship is not reported (missing), unlikely related, possibly related, or related.

## 6.5.1.2 Pre-Treatment AEs by SOC and PT

Pre-treatment AEs will be summarized by SOC and PT for treated subjects for the following endpoints:

- AEs by severity (total, mild, moderate, severe, moderate or severe, not reported)
- SAEs.

# 6.5.1.3 On-Treatment AEs by SOC and PT

On-treatment AEs will be summarized by SOC and PT for treated subjects for the following endpoints:

- AEs by severity
- TEAEs by severity
- AEs related to study drug by severity
- SAEs
- AEs leading to study drug discontinuation
- Hepatic-related AEs \*
- Cardiovascular AEs \*
- Suicidality AEs \*.

AEs of special interest are asterisked ("\*").

### 6.5.2 Laboratory Tests

Laboratory tests will be analyzed using results from the central laboratory and local laboratory tests reported on CRFs.

Tables, listings and figures (TLFs) will present results in both SI (Systeme Internationale) and United States (US) unit systems, if applicable.

LDL cholesterol and triglycerides will be analyzed as separate laboratory test parameters according to fasting status: fasting (i.e., fasting status of yes); not fasting (i.e., fasting status not equal to yes, including no, unknown, not reported, missing, etc.); overall.

Clinically significant laboratory abnormalities will be identified as grade 3 to 4 laboratory test results according to numeric laboratory test criteria in Common Technical Criteria for Adverse Events (CTCAE) Version 5.0 (2017) if available; otherwise according to Division of Acquired Immune Deficiency Syndrome (DAIDS) Table for Grading the Severity of Adult and Pediatric Adverse Events Corrected Version 2.1 (2017).

Laboratory tests of clinical interest for analyses will include the following:

- Hematology: hemoglobin#, hematocrit, red blood cell count, white blood cell count# with
  differential (including basophils, basophils/leukocytes, eosinophils, eosinophils/leukocytes,
  lymphocytes\*#, lymphocytes/leukocytes, monocytes, monocytes/leukocytes, neutrophils#,
  neutrophils/leukocytes), and platelets#
- Serum chemistry: alanine aminotransferase (ALT)#, AST#, albumin#, alkaline phosphatase (ALP)#, bicarbonate#, total bilirubin (TBL)#, calcium#\*, chloride\*, cholesterol (total)#, creatine kinase#, creatinine#, CPK (with fractionation, if available), direct bilirubin, estimated glomerular filtration rate (eGFR)# using the modification of diet in renal disease (MDRD) formula, glucose@\*, HDL cholesterol, hemoglobin A1C, indirect bilirubin, LDL cholesterol@, lactate dehydrogenase#, lipase, phosphorus, potassium#\*, protein, sodium#\*, triglycerides#, urea nitrogen, uric acid (urate)@
- Urinalysis: pH, specific gravity, ketones, nitrites, urobilinogen, urine hemoglobin, leukocyte esterase, urine protein@, and urine glucose@.

Tests marked with "\*" are bidirectional, tests marked with "#" will be graded according to CTCAE, and tests marked with "@" will be graded according to DAIDS.

By-subject listings of the following select laboratory test groups will be provided for enrolled subjects: hematology; serum chemistry; urinalysis (US units only); pregnancy (US units only); endocrinology, serology, drug screen, and miscellaneous laboratory tests (US units only). In addition, a by-subject listing of LFT values and ratios to ULN (i.e., ALT, AST, TBL and ALP) will also be provided for enrolled subjects for both US and SI units, which will display all LFT results over time for those with select LFT elevations (ALT or AST > 3 x ULN; ALP or TBL > 2 x ULN) at any time point. Listings will display toxicity grades, if applicable.

## 6.5.2.1 Laboratory Test Abnormalities

On-treatment laboratory test abnormalities will be summarized as the number and percentage of treated subjects in the following frequency tables:

• Worst (highest) on-treatment laboratory test abnormality for each graded laboratory test. Toxicity grade categories will be Grade 0, Grade 1 to 2, Grade 3 to 4, Grade 3, and Grade 4. Bidirectional tests will be assessed separately for each component (e.g., calcium, low; calcium, high).

- Laboratory test toxicity grade shift from baseline to the worst on-treatment toxicity grade for each graded laboratory test. Toxicity grade categories will be Grade 0, Grade 1, Grade 2, Grade 3, and Grade 4. Bidirectional tests will be assessed separately for each component (e.g., calcium, low; calcium, high).
- Laboratory test low/normal/high shifts from baseline to any abnormal on-treatment value for each laboratory test with normal ranges. Categories will be low, normal, and high. Note that categories do not depend on US or SI units. Subjects with both low and high values in the on-treatment analysis period will be counted in both low and high categories for that period and given laboratory test (thus, these categories are not mutually exclusive). Subjects must have only normal values in the on-treatment analysis period to be counted in the normal category for that period and given laboratory test.

Tables will present results by laboratory tests alphabetically within laboratory test group, as applicable.

### 6.5.2.2 Liver Function Test Elevations

### LFT Elevations: Cumulative, Mutually Exclusive, and Composite

The number and percentage of subjects with LFT elevations will be summarized separately for each analysis period (pre-treatment, on-treatment) for treated subjects.

The frequency table of LFT elevations will include the following endpoints:

- Cumulative elevations:
  - o ALT > 1 x, > 3 x, > 5 x, > 10 x, and > 20 x ULN
  - o AST > 1 x, > 3 x, > 5 x, > 10 x, and > 20 x ULN
  - o ALT or AST > 1 x, > 3 x, > 5 x, > 10 x, and > 20 x ULN
  - o TBL > 1 x, > 1.5 x, and > 2 x ULN
  - $\circ$  ALP > 1 x, > 1.5 x, and > 2 x ULN
- Mutually exclusive elevations:
  - ALT > ULN to  $\leq$  3 x ULN, > 3 x ULN to  $\leq$  5 x ULN, > 5 x ULN to  $\leq$  10 x ULN, > 10 x ULN to  $\leq$  20 x ULN, and > 20 x ULN
  - o AST > ULN to  $\leq$  3 x ULN, > 3 x ULN to  $\leq$  5 x ULN, > 5 x ULN to  $\leq$  10 x ULN, > 10 x ULN to  $\leq$  20 x ULN, and > 20 x ULN
  - ALT or AST > ULN to  $\le 3$  x ULN, > 3 x ULN to  $\le 5$  x ULN, > 5 x ULN to  $\le 10$  x ULN, > 10 x ULN to  $\le 20$  x ULN, and > 20 x ULN
  - o TBL > ULN to  $\leq 1.5$  x ULN, > 1.5 x ULN to  $\leq 2$  x ULN, and > 2 x ULN
  - o ALP > ULN to  $\leq 1.5$  x ULN, > 1.5 x ULN to  $\leq 2$  x ULN, and > 2 x ULN

